## 4.11 Safety Evaluation

All safety summaries and analyses will be based upon the SAF as defined in Section [4.5](#).

Safety summaries will be grouped by treatment as indicated in [Table 2](#) and [IA: Interim analysis. FA: Final analysis.](#)

### [\[1\] AE and Categorical Safety only](#)

[Table 3](#) at Section [4.2](#).

Unscheduled tests will be listed only, unless it contributes as a baseline or as a worst post-baseline value.

#### 4.11.1 Adverse Events

Adverse events (AEs) will be coded using the Medical Dictionary for Regulatory Activities (MedDRA) Version 23.0.

An AE is any untoward medical occurrence in a study subject administered an IMP which does not necessarily have a causal relationship with this treatment. An AE can therefore be any unfavorable and unintended sign (including a clinically significant abnormal laboratory finding), symptom, or disease temporally associated with the use of an IMP, whether or not considered related to the IMP. Adverse events may include the onset of new illness and the exacerbation of pre-existing conditions.

Other untoward events occurring in the framework of a clinical study will be recorded as AEs, e.g. those occurring during treatment-free periods (including Screening or post-treatment Follow-up periods), in association with study-related procedures and assessments or under placebo.

Concomitant illnesses, which existed before entry into the clinical study, will not be considered AEs unless they worsen during the treatment period. Pre-existing conditions will be recorded as part of the subject's medical history.

A treatment-emergent adverse event (TEAE) is defined as an AE that begins or worsens in severity in 28 days after study drug administration.

Adverse event with 'No Relationship' or 'Unlikely Related' causality will be evaluated as not related (relationship = No), otherwise (including missing causality) AE will be evaluated as related (relationship = Yes).

Adverse events with completely unknown start dates will be considered as treatment-emergent for the tabulations and will be shown as NK in the listings. Partially complete AE dates will not be imputed in the listings and the available day, month and year components will be used to determine if an adverse event is treatment-emergent taking the first dosing date and end of study date as references.

Solicited adverse reactions are foreseeable AEs following vaccination with GRAd-COV2 including the following AEs: injection site pain, erythema, warmth, swelling, pruritus, myalgia, arthralgia, headache, fatigue, fever, feverishness, malaise and nausea. Solicited adverse reaction is recorded as such on the corresponding AE's eCRF.

Adverse events of special interest (AESI) are any grade  $\geq 3$  abnormalities on safety blood test according to Common Terminology Criteria for Adverse Events v.5.0 (CTCAE, see section [4.11.3](#)).

An overview will be provided with the number and percentage of subjects as well as the total number of occurrences of the following event categories by treatment group:

- Any TEAE;
- Any TEAE related to study drug;
- Any treatment-emergent SAE (see section [4.11.2](#));
- Any treatment-emergent SAE related to study drug;
- Any TEAE leading to study discontinuation;
- Any AESI;
- Any solicited adverse reactions emerged in the first 7 days post dose.

Adverse event summaries by system organ class (SOC) and preferred term (PT) with number and percentage of subjects as well as the total number of occurrences will be provided by treatment group for the following:

- All TEAE;
- TEAEs by maximum severity;
- TEAEs by causality;
- All AESI;
- All solicited adverse reactions emerged in the first 7 days post dose.

Additional summary for all TEAE will be provided by PT and treatment group.

Adverse event summaries will be ordered in terms of decreasing frequency for SOC and PT within SOC in the Total group and then alphabetically for SOC and PT within SOC. Summaries will be ordered in terms of decreasing frequency for PT in the Total group in summaries where SOC is not included.

For each subject and each adverse event, the worst severity recorded will be attributed and used in the by-severity summaries. Similarly, the worst causality (most related to treatment) will be attributed and used in the by-causality summaries. If severity or causality is missing, a conservative approach for AE assessment (taking into account the worst case) will be followed.

By-subject listing of all adverse events (including non-treatment-emergent events) will be provided by treatment group. Adverse event listing will include center, subject identifier, age, sex, race, adverse event (SOC, PT, and verbatim term), date of onset, date of resolution, duration, solicitation flag, special interest flag, severity, seriousness, action taken, outcome and causality.

Adverse event listings will be provided for the following:

- All AEs
- All severe TEAE;
- All TEAE related to study drug;
- All AESI;
- All solicited adverse reactions emerged in the first 7 days post dose.

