18.	Reference.....	43

1. Synopsis

Trial Title	A Phase 1, Dose-Escalation Study to assess the Safety and Immunogenicity of a COVID-19 Vaccine GRAd-COV2 in Healthy Adults and Elderly Subjects	
Internal ref. no.	RT-CoV-2	
Clinical Phase	Phase I	
Trial Centre	Istituto per Malattie Infettive (INMI) L. Spallanzani, [name]; Coordinator Clinical Site Centro Ricerche Cliniche Verona srl c/o Policlinico G.B. Rossi [name]	
Trial Design	Open label study	
Trial Participants	(i) Healthy adult volunteers (aged 18-55) including men and non-pregnant women (ii) Elderly volunteers (aged 65-85) without significant clinical conditions	
Planned Sample Size	Arm 1: 15 Healthy younger adults volunteers (aged 18-55); 1 dose GRAd-COV2 (5×10^{10} vp) Arm 2: 15 Healthy younger adults volunteers (aged 18-55); 1 dose GRAd-COV2 (1×10^{11} vp) Arm 3: 15 Healthy younger adults volunteers (aged 18-55); 1 dose GRAd-COV2 (2×10^{11} vp) Arm 4: 15 Healthy older adults volunteers (aged 65-85); 1 dose GRAd-COV2 (5×10^{10} vp) Arm 5: 15 Healthy older adults volunteers (aged 65-85); 1 dose GRAd-COV2 (1×10^{11} vp) Arm 6: 15 Healthy older adults volunteers (aged 65-85); 1 dose GRAd-COV2 (2×10^{11} vp) Total = 90 volunteers	
Study duration	12 months	
Follow up duration	Patients will be followed up for 24 weeks after vaccination. Follow-up will include medical visit and test at day 2, day 7, week 2, week 4 week 8, week 12 and week 24	
Planned Trial Period	10 months (from screening of first participant to 6 months after final vaccination of last volunteer)	
	Objectives	Endpoints
Primary	To evaluate the safety of administering GRAd-COV2, intramuscularly in healthy (younger and older adults) volunteers	A. Occurrence of solicited local AE signs and symptoms for 7 days following the vaccination B. Occurrence of solicited systemic AE signs and symptoms for 7 days following the vaccination C. Occurrence of unsolicited AE for 28 days following the vaccination D. Change from baseline for safety laboratory measures at different time point E. Occurrence of severe AE during the whole study duration

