4.2. Endpoints

4.2.1. Primary endpoints (safety)

The primary endpoint of the study is to assess safety in term of occurrence of solicited and unsolicited adverse events (AE). Occurrence of AE will be monitored by preplanned medical visits and blood tests (active surveillance) and by recording participant's reported AE (passive surveillance). This includes:

- A. Occurrence of solicited local AE signs and symptoms for 7 days following the vaccination
- B. Occurrence of solicited systemic AE signs and symptoms for 7 days following the vaccination

- C. Occurrence of unsolicited AE for 28 days following the vaccination
- D. Change from baseline for safety laboratory measures at different 2 days, 7 days, 2 weeks, 4 week, 8 weeks, 12 weeks and 24 weeks
- E. Occurrence of serious AE (SAE) during the whole study duration

Volunteers will undergo clinical follow up for AE for 24 weeks following completion of the vaccination regimen. SAEs will be collected throughout the study.

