9.5. Reporting procedure for all AE

All local and systemic AEs occurring in the 28 days following each vaccination observed by the Investigator or reported by the participants, whether or not attributed to study medication, will be recorded. Recording and reporting of all AEs will be detailed in SOP. All AEs that result in a participant withdrawal from the study will be followed up until a satisfactory resolution occurs or until a non-study related causality is assigned (if the participant consents to this). SAEs will be collected throughout the entire trial period (i.e. until W24).

SAEs will be reported on the SAE forms by doctors who enrolled participants to the principal investigator and DSMB. SAE will be documented accurately and notified within 48 hours to the DSMB. The DSMB will also review severity and causality analysis within 2 days and will provide advice on study continuation. AEs will be reported to DSMB within 7 days. In special circumstance the chair of DSMB may decide to involve the ethical committee to analyze AE reports in order to define how to continue the study.

SAR and SUSAR that occur within week 10 of the study will determine a temporal suspension of the enrollment pending the decision of DSMB. The suspension is decided by the local investigator and immediately communicated to principal investigator and DSMB. When a SAR or a SUSAR occurs among participants enrolled in a clinical center the investigator of the clinical center will immediately contact the principal investigator who will eventually contact other enrolling centers.

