#### 4.2.2 Imputation of Missing and Incomplete Dates/Times

Every effort will be made to collect complete dates for all study assessments. The following date imputation rules will be applied for missing or partial dates:

- If month and year available, set start date to latest of (1st of the month, first dose date), if end date is complete and imputed start date > end date, set imputed start date to end date – 1
- If year available: Set start date to latest of (January 1st, first dose date), if end date is complete and imputed start date > end date, set imputed start date to end date – 1
- If start date is completely missing, set to first dose date, if end date is complete and imputed start date > end date, set imputed start date to end date – 1.

Completely missing time information will be imputed as 00:00. Partially missing time information with missing hour (xx:mm) or minute (hh:mm) part will be imputed as 00:mm or hh:00, respectively. Missing part will be shown as NK in the listings (where NK = Not Known).

If time is not collected and date of assessment is the same as the first dose date, then assessment will be assumed to be collected prior to treatment unless schedule of assessments and protocol indicate planned collection is always after dosing.

Any AEs with incomplete start and end dates/times will be treated as follows:

Adverse events with unknown start and/or end times (but where the date is known) will be imputed with a time of 00:00 h for the tabulations but will be shown as NK:NK in the listings (where NK = Not Known).

Adverse events with completely unknown start dates will be considered as treatment-emergent for the tabulations and will be shown as NK in the listings. Partially complete AE dates will not be imputed in the listings and the available day, month and year components will be used to determine if an adverse event is treatment-emergent taking the first dosing date and end of study date as references.

Imputing partial AE and prior/concomitant medication start dates:

- a) If the year is unknown, the date will not be imputed and will be assigned a missing value.
- b) If the month is unknown, then:
  1. If the year matches the first dose date, then impute to the month and day of the first dose date.
  2. Otherwise, assign 'January'.
- c) If the day is unknown, then:
  1. If the month and year match the first dose date, then impute to the day of the first dose date.
  2. Otherwise, assign '01'.

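### The SAP counts SAEs by arm only within 28 days of vaccination, although primary endpoint E covers SAEs over the whole 24-week study; later SAEs are listed but not tabulated

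*SAP*

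**What the plan says.** Protocol section 4.2.1 gives endpoint E as "Occurrence of serious AE (SAE) during the whole study duration". Section 9.5 has SAEs collected until W24, and the synopsis sets the length of follow-up: "Patients will be followed up for 24 weeks after vaccination". The synopsis words endpoint E differently, as "Occurrence of severe AE during the whole study duration", but over the same period. Endpoint C, on unsolicited AEs, is the one with a 28-day window.

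SAP section 4.11.1 uses one window for its adverse-event tables: "A treatment-emergent adverse event (TEAE) is defined as an AE that begins or worsens in severity in 28 days after study drug administration". The overview table by treatment group has two SAE rows, "Any treatment-emergent SAE" and "Any treatment-emergent SAE related to study drug". The tables by system organ class and preferred term cover TEAEs, AESI and solicited reactions, with none for SAEs or deaths.

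SAP section 4.11.2 adds separate listings of deaths and serious AEs with no treatment-emergent restriction. Section 4.11.1 lists all AEs, treatment-emergent or not. AESI, defined as grade 3 or higher safety-blood abnormalities, are tabulated with no stated time limit.

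For times, SAP section 4.2.2 says that an AE with a known date but unknown time is "imputed with a time of 00:00 h for the tabulations".

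**The concern.** The 28-day window suits endpoint C. Applied to the SAE rows, it leaves endpoint E without a numerator or percentage by arm over the period for which it is defined. A listing does not summarise occurrence by arm, and a reader of the overview table would find 20 of the 24 weeks missing from the SAE rows.

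Late SAEs are foreseeable under the documents' own rules. Protocol section 7.8 has participants with confirmed COVID-19 admitted to hospital. Protocol section 9.1 counts hospitalization of any length as an SAE, and SAP section 4.11.2 also includes hospitalization. Protocol section 15.1.3 says that follow-up should allow vaccine-mediated disease enhancement to be assessed. A COVID-19 admission in week 10 bears directly on that risk, yet would appear in neither SAE row.

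The final analysis is also meant to report safety at 24 weeks (SAP section 1). Each interim analysis runs until the last subject of its cohort completes Week 4 (SAP section 4.14). The 28-day SAE rows are then almost complete at the interims, so the final table adds almost nothing to them.

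**Working it through.** **Inputs.** TEAE window: 28 days (SAP 4.11.1). SAE collection: to W24 (Protocol 9.5). W24 visit window: ±14 days (schedules in both documents). Subjects: 6 arms × 15 = 90. Neither document gives a power or precision figure for SAEs, so there is no planned figure to reproduce.

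**1. Share of follow-up covered by the SAE counts.**
- 24 × 7 = 168 days; 28/168 = 16.7%, one sixth.
- W24 visit at its latest: 168 + 14 = 182; 28/182 = 15.4%.
- W24 visit at its earliest: 168 − 14 = 154; 28/154 = 18.2%.
- Vaccination day counted in addition to the 28: 29/168 = 17.3%.
- Protocol 7.8 also names a W48 visit that is in neither schedule. If follow-up ran to W48, the share would be 28/336 = 8.3%. The W24 figure is used here.

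**2. Where an SAE with onset after day 28 appears.**

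| Planned output | Appears? |
|---|---|
| Overview rows for SAEs and related SAEs (SAP 4.11.1) | No |
| TEAE tables by SOC/PT, severity and causality (SAP 4.11.1) | No |
| AESI tables (SAP 4.11.1) | Only if a grade ≥3 laboratory abnormality |
| Listings of deaths and serious AEs (SAP 4.11.2) | Yes |
| Listing of all AEs (SAP 4.11.1) | Yes |

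The AESI row matters because Protocol 9.1, item F, counts grade 3 or higher safety-blood abnormalities as SAEs. That part of endpoint E is tabulated beyond day 28.

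**3. Illustration of what the counts would show.** The documents give no SAE rate. Assume a 24-week risk p per subject of 1% to 10% and a constant hazard. Then p28 = 1 − (1 − p)^(28/168), and the chance of at least one subject with an SAE among n is 1 − (1 − risk)^n. For p = 3% and n = 90: p28 = 1 − 0.97^(1/6) = 0.00506; expected subjects 90 × 0.00506 = 0.46; chance of at least one 1 − 0.97^15 = 37%. Over 24 weeks: 90 × 0.03 = 2.7 and 1 − 0.97^90 = 94%.

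| Assumed 24-week risk | Expected subjects, 28 days | Expected subjects, 24 weeks | Chance of ≥1, 28 days | Chance of ≥1, 24 weeks |
|---|---|---|---|---|
| 1% | 0.15 | 0.9 | 14% | 60% |
| 3% | 0.46 | 2.7 | 37% | 94% |
| 5% | 0.77 | 4.5 | 54% | 99% |
| 10% | 1.57 | 9.0 | 79% | about 100% |

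Within one arm of 15, at 3%, the chance of at least one is 7% over 28 days and 37% over 24 weeks.

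**4. Vaccination-day AEs with unknown time.** Take a dose at 10:00 (assumed) and an AE on the same date imputed to 00:00. Compared as date-times, the AE precedes the dose and is not treatment-emergent. Compared as dates, it falls on the dose date and is. The SAP does not say which comparison applies. Study day is derived from dates (SAP 4.2), the TEAE window is in days, and partial AE dates are compared by calendar components (SAP 4.11.1), all of which point to dates.

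**The case against.** The strongest reply is that nothing is lost. Every SAE to W24 is in a listing with treatment group, seriousness and causality. In a descriptive study of 90 subjects with no formal testing, late SAEs can be counted from it by hand. The row label also says treatment-emergent, so a careful reader knows its limit. This stands as far as it goes: the gap is a missing table and not missing data. It does not supply the planned numerator and percentage by arm that a primary endpoint should have.

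Four stronger readings are tempting and are not supported.

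- A reader might infer that endpoint E itself is cut to one sixth. Only its tabulation is, and the AESI part of it carries no stated limit.
- A reader might infer that five of every six SAEs are left out. One sixth is a share of time; it is a share of SAEs only under a constant hazard.
- A reader might infer that AEs leading to discontinuation are equally hidden. Those rows and that listing are restricted to TEAEs, but SAP section 4.4.1 summarises withdrawals by reason without a 28-day limit, and discontinuation is not a primary endpoint.
- A reader might infer that the 00:00 rule removes first-day reactions. It touches only AEs with a known date and unknown time, and matters only if date-times are compared. Solicited reactions have their own eCRF flag and their own 7-day tables, which are not defined through TEAE.

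**Conclusion.** The point holds for the planned tables. As written, the SAP tabulates SAEs and related SAEs by arm over 28 of 168 days (16.7%; 15% to 18% with the W24 window), while the primary endpoint covers the whole study. Later SAEs appear only in listings, except grade 3 or higher laboratory abnormalities. This rests on the text alone and on W24 as the end of SAE collection. The expected counts and probabilities above are illustrations under assumed risks and a constant hazard, not predictions.

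A zero in the SAE row, 0/90, has an exact two-sided 95% upper limit of 1 − 0.025^(1/90) = 4.0%. That bound would describe the 28-day risk only. The SAP plans no interval for this row, so a misreading as a whole-study bound is possible but not built into the plan.

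The 00:00 imputation is a matter for clarification and not a demonstrated error.

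**What to change.** - In SAP section 4.11.1 or 4.11.2, add for the final analysis a table by arm with the number and percentage of subjects and the number of events for all SAEs, related SAEs and deaths, from vaccination to W24, split at day 28. State whether vaccination day counts within the 28 days.
- Keep the 28-day window for endpoint C.
- Minor clarification in SAP section 4.2.2: AEs on the vaccination date with unknown start time count as treatment-emergent unless recorded as pre-dose.
- While editing, reconcile three related texts: severe (synopsis) against serious (section 4.2.1) in protocol endpoint E; the W48 visit in protocol section 7.8 against the schedules; and the end-of-study reference for partial AE dates in SAP section 4.11.1 against the 28-day definition. Under that last rule, a partly dated late event might count where a fully dated one would not.

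The cost is SAP wording and a few added table rows. The data are already collected to W24, so no visit, form or sample changes.

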#### **4.11.2 Deaths, Serious Adverse Events, and Other Significant Adverse Events**

A serious AE (SAE) is defined as an AE which fulfills one or more of the following criteria: is a medically significant event (examples of such medical events include allergic reaction requiring intensive treatment in an emergency room or clinic, blood dyscrasias, or convulsions regardless eventual need of hospitalization), is a congenital anomaly/birth defect, requires hospitalization or prolongation of existing hospitalization, causes persistent or significant disability or incapacity, is a life-threatening event or results in death. Serious adverse event is recorded as such on the corresponding AE's eCRF.

Separate AE listings will be provided for the following:

- Deaths;
- Serious AEs;

- TEAEs leading to study discontinuation.

Listings format will follow format described for adverse events in Section 4.11.1.

#### 4.11.3 Clinical Laboratory Evaluation

Safety laboratory evaluations (hematology, biochemistry and urinalysis) will be assessed as shown in the Schedule of Assessments (Appendix 6.1). For list of safety laboratory test parameters refer to Blood test and other analysis for monitoring safety (section 8.3) in study protocol.

Urinalysis results will be listed only.

Hematology and biochemistry results will be graded according to NCI CTCAE (Version 5.0). Individual CTCAE grades will be provided with the by-subject listings.

For each hematology and biochemistry parameter:

- Results and change from baseline will be summarized descriptively by visit and treatment group;
- Number and percentage of subject in normal range categories will be tabulated by visit and treatment groups.
- Number and percentage of subject in each CTCAE severity grades will be tabulated by visit (and overall) and treatment groups.

Worst post-baseline record will be selected (flagged) by utilizing the rules as follow:

If there is any LOW or HIGH record, flag the most extreme record. Most extreme record will be derived by using the factor (f) for corresponding normal limits as appropriate ( $f \times LLN$  or  $f \times ULN$ ). If there are multiple records with most extreme value, flag the earliest occurrence. If not out of normal range results is observed flag the first post-baseline observation.

By-subject listing of hematology and biochemistry with change from baseline will be provided by dose and time point for each treatment group separately.

All values outside the clinical reference ranges will be flagged in the data listings. The abnormal values will be flagged with 'L' for values below the lower limit of the clinical reference range and 'H' for values above the upper limit of the clinical reference range and included in the listings. The Investigator will assess whether the values outside the clinical reference range are clinically

significant (CS) and these will be reported as abnormal NCS or abnormal CS. Clinically significant laboratory values will be recorded by the Investigator as AEs.

#### 4.11.4 Liver Safety

Based on the maximum post baseline value, the following criteria will be used to categorize the liver function tests, according to the Upper Limit of Normality (ULN):

- ALT  $\geq 3X$ ,  $\geq 7.5X$ ,  $\geq 10X$  and  $\geq 20X$  ULN
- AST  $\geq 3X$ ,  $\geq 5X$ ,  $\geq 10X$ , and  $\geq 20X$  ULN
- AST and/or ALT  $\geq 3X$  ULN
- Total Bilirubin  $\geq 2X$  ULN
- ALT and/or AST  $\geq 3X$  ULN and Total Bilirubin  $\geq 2X$  ULN (Hy's law)

For the ALT and/or AST  $\geq 3X$  ULN and Total Bilirubin (TBL)  $\geq 2X$  ULN criterion, a subject's ALT and Total Bilirubin laboratory draw date or AST and Total Bilirubin laboratory draw date must occur on the same date to be considered.

Frequency tables showing the number and percentage of subjects with potentially clinically significant values in liver function tests after first dose administration in the study will be provided.

A listing of the subjects meeting any of the criteria will be provided.

Helping visualization of possible Hy's law cases, an Evaluation of Drug Induced Serious Hepatotoxicity (eDISH) plot will be provided for post-baseline biochemistry results.

